10. DISCONTINUATION FROM SAMPLE COLLECTION AND FOLLOW UP

Patients may discontinue from sample donation at any time at their own request, or they may be discontinued at the discretion of the Principal Investigator. If all three of the baseline (pre-RT/CRT), RT week 1 and RT week 2 samples are not collected, the patient will be withdrawn from the study and an additional patient recruited.

If a patient wishes to withdraw from the study and has donated both baseline and 12 week blood samples it should be clarified whether they no longer wish to donate any further samples but agree that information about them may still to be sent to the ICR-CTSU, or whether they have withdrawn consent for further information about them to be collected within the study. A 'Change of Study Status' form should be submitted to ICR-CTSU stating the nature of withdrawal.

Should a patient withdraw consent for their samples to be used in INOVATE their blood samples will be destroyed and tissue samples returned to the site for archiving following receipt of written confirmation from the site to ICR-CTSU.

11. BIOLOGICAL SAMPLE PROCESSING AND ANALYSES

All samples will be transported to the central ICR laboratory for storage within 48-72 hours. Samples will be pseudo-anonymised and allocated a unique study reference number. All samples will be processed and analysed in accordance with Good Clinical Practice Laboratory (GCLP) standards using pre-defined standard operating procedures (SOPs). The laboratory staff will be blinded to the clinical data including the HPV status.

11.1 Tissue samples

Tumour will be identified from the formalin fixed paraffin-embedded (FFPE) tissue samples and DNA will be isolated using micro dissection. DNA and RNA will be extracted from the plasma using a standard, commercially available Qiagen Circulating Nucleic Acid kit.

11.2 Plasma samples

The collected blood (Streck^m tubes) will be centrifuged (1600 rpm X 20 min) on receipt at the central laboratory. 1 mL of plasma will be aliquoted into separate cryovials labelled as per the sample bottle. Buffy coat will be separately aspirated and stored. The plasma will be frozen at -80°C and stored at the ICR. Prior to extraction, plasma samples will be further centrifuged at 14000 rpm for 10 minutes. DNA and RNA will be extracted from 5mL of plasma and buffy coat using the QIAamp Circulating Nucleic Acid Kit (Qiagen) according manufacturer's instructions. DNA and RNA will be eluted in 50 μ L of AVE buffer at stored at -20°C.

11.3 Tumour Characteristics

11.3.1 DNA quantification and sequencing (tissue and plasma)

Plasma and tissue DNA will be quantified using a Bio-Rad QX100 ddPCR machine- using ribonuclease P (RNase P) as a reference gene. This will be sequenced for HPV DNA using HPV-detect. Samples will be classified into HPV DNA positive and negative based on the thresholds generated in the pilot study (*Lee, Br J Cancer, 2017*).

11.3.2 RNA analysis

RNA will be extracted from biological samples (tumour tissue and plasma samples (buffy coat) and will be subjected to high-throughput techniques such as RNA-sequencing or other molecular techniques to identify changes relevant to cancer biology and resistance to treatment. The analysis will focus initially on the identification of genomic changes in the tumour, which can be identified in the contemporaneous plasma samples (buffy coat) at the outset of treatment. The changes will then be followed in a longitudinal manner throughout treatment in plasma and other biological samples. This will allow analysis for exploratory endpoints.

12. STATISTICAL CONSIDERATIONS

12.1 Statistical Design and Sample Size Justification

The primary aim of the proposed study will be to establish the potential of HPV-detect to predict absence of residual disease (high specificity). To demonstrate specificity compared with ¹⁸F-FDG PET-CT of at least 85%, assuming that the true specificity is 95%, then with 80% power, given two-sided type I error of 0.05 and assumed prevalence of residual disease of 25% on ¹⁸F FDG PET-CT, the study will require recruitment of 100 HPV+ oropharyngeal cancer patients undergoing RT/CRT. Assuming a rate of patient dropout and sample loss of 30%, 143 HPV+ oropharyngeal cancer patients will need to be registered into the study. Forty-eight (N=143/3≈48) HPV- oropharyngeal cancer patients will also be recruited as negative controls to demonstrate that plasma HPV DNA is not seen sporadically in this patient group. This number will allow estimation of an upper one-sided 95% confidence bound of 6%, given proportion observed of 0% in HPV- oropharyngeal cancer patients 191 patients.

12.2 Endpoint Definitions

12.2.1 Primary endpoint

The specificity of HPV-detect (using plasma HPV DNA levels) in correctly identifying those with no residual disease, at 3 months following completion of primary RT/CRT is defined as the proportion patients who are HPV-detect negative among those with no residual disease according to 18F-FDG PET-CT at the same time point.

12.2.2 Secondary endpoints

- The sensitivity of HPV-detect (using plasma HPV DNA levels) in correctly identifying those with residual disease at 3 months following completion of primary RT/CRT, is defined as the proportion of patients who are HPV-detect positive among those with residual disease according to ¹⁸F-FDG PET-CT at the same time-point.
- The proportion of patients who have no residual disease on biopsy/neck dissection amongst those with residual disease according to 18F FDG PET-CT but HPV-detect negative at 3 months after primary RT/CRT.
- Repeated measures of plasma HPV DNA levels up to a period of 12 months post RT/CRT (time points defined in the protocol) will be associated with the clinical and radiological response.
- Sensitivity and specificity of HPV-detect in measuring plasma HPV DNA levels compared with HPV DNA levels from diagnostic tissue at baseline are defined as the proportions of true positives and the proportions of true negatives, respectively.
- The pattern of plasma HPV DNA responses to RT/CRT will be presented by calculating the percentage change in HPV DNA level at each assessment time points from baseline.

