2. BACKGROUND AND RATIONALE

In the last decade, Human Papilloma Virus (HPV) related head and neck cancer has been proven to be a distinct disease entity in terms of epidemiology, tumour biology and response to treatment. The UK incidence of locally advanced human papilloma virus related oropharyngeal cancer (HPV+ oropharyngeal cancer) is 2000/year (Office of National Statistics in England, NHS National Services Scotland, Northern Ireland Cancer Registry, and Welsh Cancer Intelligence & Surveillance Unit). At least 50% of patients present with stage III/IV disease (AJCC 7) – so-called locally-advanced head and neck cancer (LAHNC)[1]. Organ-preserving radiotherapy (RT), or concomitant- cisplatin-based chemoradiotherapy (CRT), followed by surgical salvage if required, is a standard-of-care for LAHNC of the oropharynx[2] and, compared to conventional surgery, achieves equivalent or improved locoregional control and disease-free survival rates with favourable functional outcomes[3, 4]. Following RT/CRT, decisions regarding salvage surgery for residual primary and cervical lymph node disease are based on clinical examination and imaging. ¹⁸F-FDG PET-CT, when available, is the imaging modality of choice[5], with a negative predictive value in excess of 90%[5, 6]. However, the positive predictive value is sub-optimal and 20-30%[7] of patients frequently undergo unnecessary (no viable tumour on post-operative pathology) neck dissection (ND)[8] and/or repeated biopsies from the purportedly residual primary tumour. ND causes significant morbidity (fibrosis, facial/hypoglossal nerve damage, reduced shoulder movement, swallowing problems)[9-12] and repeated biopsies to rule out residual cancer at the primary site can lead to delayed mucosal healing and significant patient anxiety. Furthermore, HPV+ patients are younger and due to the excellent treatment outcomes with the current treatments are expected to carry the burden of treatment related toxicity for life. Over the last few decades, the incidence of HPV+ oropharyngeal cancer has significantly increased and is projected to increase by up to 230% in the near future[13, 14]. Therefore, optimised predictors of residual disease are required as a means of guiding management decisions.

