HPV DNA is released into the bloodstream and can potentially be used as a detection marker of HPV+ oropharyngeal cancer. In a recently completed single-centre prospective pilot study a novel next generation sequencing assay (HPV-detect) was developed for the detection of circulating HPV DNA (cHPV-DNA)[15].

A pilot study performed at the Royal Marsden Hospital/Institute of Cancer Research prospectively collected serial plasma samples in test (n=41) and independent validation cohorts (n=33) of a homogeneous group of patients with non-oral cavity LAHNC treated with primary chemo-radiotherapy. The validation cohort consisted of a separate set of patients with LAHNC, treated identically to patients in the test cohort. Pre-treatment tumour HPV status was confirmed using E7 PCR (gold standard)[16]. Circulating HPV DNA levels at 12 weeks post-CRT/CRT were correlated to residual disease assessed by ¹⁸F-FDG PET-CT and surgery[16].

In the test cohort (of which 27 were HPV+), HPV-detect demonstrated 100% sensitivity and 93% specificity in detecting HPV DNA in baseline (pre-treatment) plasma samples compared with tumour biopsy HPV status. In the corresponding plasma samples in the validation cohort (of which 20 were HPV+), HPV-detect demonstrated 90% sensitivity and 100% specificity compared with tumour biopsy HPV status. 38 HPV+ patients (test & validation cohort) had pre-treatment and 12 weeks post-treatment plasma samples-set available. Thirty patients had a negative HPV-detect and negative ¹⁸F-FDG PET-CT at the end of treatment and required no further treatment. In 7 patients a positive ¹⁸F-FDG PET-CT post treatment indicated residual disease in the cervical lymph nodes (n=4) or at site of primary disease (n=3). The 4 patients with ¹⁸F-FDG PET-CT

CT uptake in lymph nodes underwent a ND, which did not show pathological evidence of viable cancer. Three patients with ¹⁸F-FDG PET-CT uptake at primary site underwent repeated biopsies that were all negative for residual cancer. All seven patients had undetectable HPV DNA in the plasma samples at the end of treatment. Therefore, HPV DNA can potentially predict for the "true" absence of residual disease in patients with positive or equivocal ¹⁸F-FDG PET-CT. The inclusion of plasma HPV DNA levels in addition to ¹⁸F-FDG PET-CT to the algorithm for diagnosis of presence of residual disease following potentially curative treatment will help avoid unnecessary ND and tumour biopsies.

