8.4 Clinical Data Collection

Electronic (e) Case Report Forms (CRFs) will be used for the collection of study data. Clinical data will be stored and analysed at ICR-CTSU who will provide guidance to sites to aid the completion of the eCRFs.

The following data will be collected on electronic case report forms:

At baseline: age, sex, smoking history, detailed tumour staging, HPV (p16Ink4A) status.

Post RT/CRT treatment: radiotherapy start date and schedule.

At 12 week post RT/CRT: results of 12 week ¹⁸F FDG PET-CT scan (and any repeated scans), carried out as per local practice for assessment of local control. If an HPV+ patient is found to have residual disease at the 12 week assessment and is scheduled to receive surgery/biopsy this should be reported to the ICR-CTSU trials office in an expedited fashion on the appropriate eCRF as soon as the surgery/requirement for biopsy is is confirmed.

During follow up: Information on the status of disease recurrence will be collected at 3, 6, 9 and 12 months post-RT/CRT. It is anticipated that further radiological review will be carried out as per standard practice if clinical assessment raises the suspicion of recurrent disease.

9. PROCEDURE FOLLOWING CONFIRMATION OF RESIDUAL DISEASE (AT 12 WEEKS), DISEASE PROGRESSION OR RECURRENCE

If the confirmation of residual disease following the 12 week ¹⁸F FDG PET-CT scan or later confirmation of disease progression/recurrence will require the patient to undergo surgery/biopsies this should be reported to the ICR-CTSU trials office in an expedited manner on the appropriate eCRF.

It is anticipated that patients with residual disease, disease progression or recurrence who meet the following criteria following radiological assessment will undergo neck surgery:

a) positive PET-CT and/orb) equivocal PET-CT with lymph node > 1cm.

If the 12 week ¹⁸F FDG PET-CT scan is repeated following equivocal results, details of the repeat scan should be notified to ICR-CTSU on the appropriate eCRF.

It is anticipated that patients who have residual disease at primary site will undergo a biopsy of this site. However if the 12 week ¹⁸F FDG PET-CT scan is repeated (according to local practice) following equivocal results, details of the repeat scan should be notified to ICR-CTSU on the appropriate eCRF.

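### The histology endpoint takes a negative biopsy as final and leaves the 12-month recurrence status unused, so any cancer missed by biopsy favours HPV-detect; a cheap improvement is available

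*Protocol*

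**What the plan says.** Protocol 12.2.2 lists as a secondary endpoint "The proportion of patients who have no residual disease on biopsy/neck dissection amongst those with residual disease according to" PET-CT who are HPV-detect negative at 3 months. Section 12.3 analyses it in the same population and manner as the primary endpoint, as a proportion with an exact 95% confidence interval. Neither section gives a negative biopsy and a negative neck dissection different standing, and neither brings later follow-up into the definition.

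On biopsies, the Background (Section 2) says that "repeated biopsies to rule out residual cancer at the primary site can lead to delayed mucosal healing and significant patient anxiety". Of the pilot, it reports that the three patients with "uptake at primary site underwent repeated biopsies that were all negative for residual cancer", and that "All seven patients had undetectable HPV DNA in the plasma samples at the end of treatment". For this study Section 9 states: "It is anticipated that patients who have residual disease at primary site will undergo a biopsy of this site". Section 9.1 B compares histology with imaging in a random 20% of neck dissections; no such check is stated for biopsies.

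On follow-up, Section 4.2 collects recurrence status at 3, 6, 9 and 12 months. Section 12.3 plans to relate HPV DNA over one year to disease outcome, as an analysis separate from this endpoint.

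**The concern.** The primary endpoint and the 3-month sensitivity endpoint both take PET-CT as the reference, so neither can show HPV-detect to be right where PET-CT is wrong. Yet the rationale in Section 2 is that PET-CT's positive predictive value is poor and that a negative HPV-detect could spare PET-positive patients a neck dissection or biopsy. Among the 3-month endpoints, only this one tests that claim against histology.

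A biopsy samples part of a site, whereas a neck dissection removes the abnormal node. If a biopsy misses cancer, the patient is recorded as free of disease. Because the denominator holds only HPV-detect negatives, that error is always scored as a success for the test. The data that could expose some of these errors are already collected but do not enter the endpoint.

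**Working it through.** **1. The plan's own figures.** Section 12.1 needs 100 evaluable HPV+ patients and registers 143. An exact one-sample binomial test of 85% against 95%, with upper-tail alpha 0.025, needs 75 PET-negative patients (success at 70 or more; attained alpha 0.0234, power 0.828). Then 75/0.75 = 100, and 100/0.70 = 142.9, rounded up to 143. Both figures reproduce. The histology endpoint has no sample size or target of its own.

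**2. Size of the group.** At the 25% prevalence in 12.1, 100 × 0.25 = 25 patients are PET-positive. This is a ceiling, because the endpoint keeps only the HPV-detect negatives among them. In the pilot, 7 of 7 PET-positive patients were HPV-detect negative.

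**3. Share judged by biopsy.** In the pilot 3 of 7 PET-positive patients had primary-site uptake and were biopsied: f = 3/7 = 42.9%, or 25 × 3/7 = 10.7 patients here. Seven patients are a thin basis for this share.

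**4. Bias formula.** Let q be the true residual-disease rate in the group and s the biopsy miss rate. Suppose q is the same at both sites, neck dissection misses nothing and there are no false-positive biopsies. Then

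expected proportion = (1 − q) + q × f × s, so the overstatement is q × f × s.

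The documents give neither q nor s. Assumed ranges: q = 10–30%, s = 10–40%.

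| q | s = 10% | s = 40% |
|---|---|---|
| 10% | 0.43 points (0.11 of 25) | 1.71 points (0.43 of 25) |
| 20% | 0.86 points (0.21 of 25) | 3.43 points (0.86 of 25) |
| 30% | 1.29 points (0.32 of 25) | 5.14 points (1.29 of 25) |

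For example, 0.30 × 0.429 × 0.40 = 0.0514. If every patient were judged by biopsy (f = 1), the range would be 0.10 × 0.10 = 1 point to 0.30 × 0.40 = 12 points.

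**5. Is the range for q plausible?** The pilot found no viable cancer in 7 of 7 (exact 95% CI 59.0–100%). Residual disease up to 100 − 59 = 41% is therefore not excluded, but nor is a rate near zero, at which the bias vanishes.

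**6. What one patient does.** At the ceiling, 25/25 = 100% (exact 95% CI 86.3–100). Reclassifying one negative biopsy as missed cancer gives 24/25 = 96% (79.6–99.9). The lower limit falls by 86.3 − 79.6 = 6.7 points.

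**The case against.** The case against is substantial, and much of it stands.

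- **A reader might infer that the protocol itself says primary-site disease takes repeated biopsies to rule out.** It does not. Section 2 mentions them as a burden, next to unnecessary neck dissection, and the pilot text only reports what three patients underwent. Nothing says one biopsy is insufficient.
- **A reader might infer that the first negative biopsy settles the outcome.** No such rule is written. Sections 8.1 and 9 speak of biopsies in the plural, and on a natural reading of 12.2.2 a positive repeat would count as residual disease.
- **A reader might fear that a neck specimen could clear a patient with primary-site uptake.** Section 9 anticipates that "patients who have residual disease at primary site will undergo a biopsy of this site", and Section 9.1 directs neck surgery at the PET-abnormal nodes. The anticipated procedures already link specimen and site.
- **Follow-up is not ignored.** Section 12.3 relates HPV DNA to outcome over one year in these same patients. That may bring a missed cancer to light, but it does not correct the histology proportion.
- **Detail may lie in the SAP.** Section 12.3 defers full analysis details to it, and it is not shown. What counts as absence of disease, however, belongs to the endpoint definition, which the protocol does state.
- **The size is assumed and modest.** At 25 of 25, the exact interval (86.3–100%) is wider than the largest bias in the table. But sampling error runs both ways, and this error runs in one direction only.
- **Another bias may run the other way.** The protocol does not say how PET-positive patients without any histology are counted, and that could lower the proportion.
- **Replacing histology with a mixed reference would bring its own error.** This is a fair point, and it argues for adding a second figure rather than substituting one.

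**Conclusion.** The point holds as a cheap improvement to one descriptive secondary endpoint. As defined, the endpoint accepts a negative biopsy on the same footing as a negative neck dissection and makes no use of recurrence data already in hand. Any cancer missed by biopsy therefore raises the proportion in favour of HPV-detect.

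The direction follows from the definition. The size does not: about 0.4 to 5 percentage points, or about 0.1 to 1.3 patients of 25, rests on assumed values of q and s and on a primary-site share taken from seven pilot patients. The documents do not support the stronger conclusion that the endpoint is invalid or breaks a biopsy standard set by the protocol. The primary specificity endpoint, which uses PET-CT as its reference, is untouched.

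**What to change.** In 12.2.2 and 12.3, and in the SAP:

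1. Keep the histology-only proportion as it is.
2. Add the same proportion with follow-up confirmation. A patient with a negative result on biopsy alone counts as free of residual disease only if no local or regional recurrence is recorded at 6, 9 or 12 months. State how patients without complete follow-up are classified.
3. Report biopsy-only and neck-dissection patients separately as well as together.

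Cost: a wording change, and possibly a site-of-recurrence field, since Section 4.2 promises recurrence status but not site; Section 15.2 allows eCRF additions without a protocol amendment. The confirmed figure is available only at 12 months, while the histology-only figure keeps its present timing. Some genuinely new recurrences will be counted as residual disease, which errs against the test and is therefore conservative. No extra procedure and no change to clinical management is involved.

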12.2.3 Exploratory endpoints

- Description of clinical pathway maps with a view to implementing the assay in clinical practice.
- Cost-effectiveness of the test for future implementation into clinical practice.
- Changes in molecular features between the paired tumour tissue and plama samples (buffy coat)

12.3 Statistical Analysis Plan

Analysis of the primary endpoint will include all patients in the HPV+ oropharyngeal cancer cohort who are evaluable i.e. have both HPV-detect (plasma DNA) and ¹⁸F-FDG PET-CT results at 3 months following completion of primary RT/CRT. Specificity will be calculated and presented with associated exact 95% confidence interval. Primary analysis will be performed when the last patient registered has reached the 3-month time point. Sensitivity will be analysed similarly.

Based on the high negative predictive value of HPV detect (>90%), a small proportion of patients with residual disease as per ¹⁸F-FDG PET-CT will potentially have a negative HPV-detect. We will report these as a proportion with associated exact 95% confidence intervals.

We will not alter the clinical management of these patients, but aim to collect samples for all patients up to one year, to track HPV DNA in these patients and correlate this to disease outcome.

Secondary endpoints of sensitivity, and the proportion of patients with no residual disease on biopsy/neck dissection amongst those with residual disease according to 18F FDG PET-CT but HPV-detect negative at 3 months following completion of primary chemo-radiation will be analysed using the same patient population and as per the primary endpoint. The proportions will be presented with associated exact 95% confidence interval

Association between plasma HPV DNA levels at different timepoints and clinical and radiological response up to a period of 12 months post-RT/CRT will be investigated using logistic regression models.

Analysis of sensitivity and specificity of HPV-detect in measuring HPV DNA levels at baseline will be calculated and presented with associated exact 95% confidence interval from all patients with paired data from diagnostic tissue and HPV-detect at baseline and will include both HPV+ and HPV- (negative control) patients.

Analysis of the molecular features/characteristics of the tumour tissues and to determine changes/conservation of these features in paired plasma samples.

Kinetics of change in plasma HPV DNA levels during and immediately following RT/CRT will be displayed graphically, separately for HPV+ and HPV- patients.

Full details of analyses of all primary and secondary endpoints will be described in the Statistical Analysis Plan in accordance with ICR-CTSU Standard Operating Procedures.

NIHR-DEC will undertake health-economic, stakeholder, end-user and downstream pathway analysis. Details of this will be fully developed in a specific Analysis Plan.

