| Tissue Collection | All patients: archival diagnostic tumour blocks (alternatively 5 paraffin slides or tumour DNA, if extracted for another study, may be provided for patients if the blocks are not available). HPV+ patients only: additional tissue blocks will be collected after any surgical procedure and/or biopsies which are taken post chemo-radiotherapy. | | |
| Blood Sample Collection | HPV+ patients: blood samples will be collected pre-RT/CRT, weekly during RT/CRT, at each standard clinic visit during the 4 weeks thereafter*, and at 6 weeks, 3, 6, 9 and 12 months post-RT/CRT. Additional blood samples will also be obtained for HPV+ patients before and after any surgical procedures or biopsies performed post-RT/CRT. *blood samples should be collected during this time in line with the 'standard of care' clinic visits at each site. HPV- patients: blood samples will be collected pre-RT/CRT, at 6 weeks, and at 3,6,9,12 months post-RT/CRT only. All blood samples for all patients will be collected in Streck™ tubes. | | |

| Follow up | Clinical data will be collected from routine clinical follow-up. Information on the status of |
|-----------|---|
| | disease recurrence will be collected at 3, 6, 9 and 12 months post-RT/CRT. |

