8.1 Tissue Collection

All patients: archival diagnostic tumour paraffin blocks will be collected once the site has completed standard pathological assessment and pathology guided management plans have been formulated. If the tumour blocks are not available sites may provide 5 paraffin slides or tumour DNA if extracted for another study.

HPV+ patients only: additional tissue blocks will be collected after any surgical procedure and/or biopsies which are taken post chemo-radiotherapy.

Table 1: Sample collection timepoints

| | HPV p | ositive | HPV n | egative |
|---|--------------|---------|--------------|---------|
| | Blood | Tissue | Blood | Tissue |
| Sample collection timepoints | sample | Sample | Sample | Sample |
| Baseline (study entry) i.e. after registration, before treatment | \checkmark | ~ | ✓ | ✓ |
| Weeks 1 - 6* (every week during treatment) | \checkmark | | | |
| At each standard clinic visit during the 4 weeks after treatment | \checkmark | | | |
| 6 Weeks after the end of treatment | | | \checkmark | |
| 3 Months after the end of treatment | | | \checkmark | |
| 6 Months after the end of treatment | | | ✓ | |
| 9 Months after the end of treatment | | | ✓ | |
| 12 Months after the end of treatment | | | ✓ | |
| Before any necessary biopsies or surgery | \checkmark | | | |
| After any necessary biopsies or surgery | ✓ | ~ | | |

*If radiotherapy treatment extends into week 7 sites are requested to collect an additional sample at the end of treatment.

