8.2.2 Sample scheduling and missing samples

- Weekly blood samples collected during RT/CRT for HPV+ patients should be collected on the same day each week where possible.
- Where HPV+ patients have their radiotherapy treatment extended into week 7 it is requested that an additional blood sample is collected at the end of RT/CRT treatment.
- For HPV- patients only if the baseline sample is not collected prior to RT/CRT treatment, the patient should be withdrawn from the INOVATE study.
- For HPV+ patients only if the baseline sample is not collected prior to RT/CRT treatment and both the RT week 1 and RT week 2 samples are missing, the patient should be withdrawn from the INOVATE study.
- Patients who miss sample collection at any of the time-points (other than missing all three of: baseline, RT week 1 and RT week 2) will continue in the study and will be included in final analysis.
- As the 12 week post-RT/CRT blood sample informs the primary endpoint it may be collected anytime between 11 18 weeks post-RT/CRT.
- If a patient is found to have residual disease, recurrence or progression the blood samples should still be collected according to the time lines specified in the protocol.
- If the patient does not complete RT for any reason, they should be withdrawn and sample collection will cease.

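### The planned HPV- kinetics display has no samples during treatment or in the 4 weeks after it, and percentage change from baseline fails for nearly all controls and a few HPV+ patients

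*Protocol*

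**What the plan says.** The kinetics of plasma HPV DNA are a listed secondary endpoint (Protocol sections 1 and 5.2). Section 12.3 gives the analysis: "Kinetics of change in plasma HPV DNA levels during and immediately following RT/CRT will be displayed graphically, separately for HPV+ and HPV- patients". Section 12.2.2 gives the measure, which is obtained by "calculating the percentage change in HPV DNA level at each assessment time points from baseline".

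The sampling schedules of the two cohorts differ. For the tumour-positive cohort, section 1 says "HPV+ patients: blood samples will be collected pre-RT/CRT, weekly during RT/CRT, at each standard clinic visit during the 4 weeks thereafter", and then at 6 weeks and 3, 6, 9 and 12 months. For the controls it says "HPV- patients: blood samples will be collected pre-RT/CRT, at 6 weeks, and at 3,6,9,12 months post-RT/CRT only". Table 1 in section 8.1 agrees: the rows "Weeks 1 - 6* (every week during treatment" (the on-treatment row) and "At each standard clinic visit during the 4 weeks after treatment" are ticked for blood in the HPV+ cohort alone.

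Section 8.2.2 deals with missing baselines differently in the two cohorts. For controls: "For HPV- patients only if the baseline sample is not collected prior to RT/CRT treatment, the patient should be withdrawn from the INOVATE study". An HPV+ patient without a baseline sample is withdrawn only if the week 1 and week 2 samples are missing as well. The general rule, "Patients who miss sample collection at any of the time-points (other than missing all three of: baseline, RT week 1 and RT week 2"), keeps all other patients in the study and in the final analysis.

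**The concern.** The analysis text promises a display for a group and a time window in which the schedule collects nothing. An SAP, which is not at hand, could set aside that sentence but could not carry it out.

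The measure is a separate difficulty. Percentage change divides by the baseline level, so it needs a baseline that is both measured and above zero. The controls are enrolled on the premise that they have no circulating HPV DNA, some HPV+ patients may be undetectable before treatment, and some may have no baseline sample at all.

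At stake is a descriptive secondary endpoint supported by weekly blood draws in the HPV+ cohort. If the text stands, the analyst has to depart from the protocol after the data are in, and the number of patients behind the curve may go unreported.

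**Working it through.** The protocol states no figure for this endpoint, so there is none to reproduce. The check compares the schedules and then sizes the groups for which the measure fails.

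**1. Schedules side by side (section 1; section 8.1, Table 1)**

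| Time point | HPV+ | HPV- |
|---|---|---|
| Baseline | yes | yes |
| Weeks 1 to 6 on treatment | yes | no |
| Clinic visits in the 4 weeks after treatment | yes | no |
| 6 weeks; 3, 6, 9, 12 months | yes | yes |

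The HPV+ entries in the last row come from section 1; Table 1 was not relied on for them. The time points missing for HPV- patients are every on-treatment point and every post-treatment point before 6 weeks. The 48 controls together give 0 samples in that window.

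**2. The measure**

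Percentage change at time t = 100 × (L_t − L_0) / L_0, where L_0 is the baseline level. It is undefined if L_0 is zero or missing. If L_0 is a small reading below the positivity threshold, it can be calculated but says little.

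**3. Controls**

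Section 2 gives pilot baseline specificity of 93% in the test cohort (41 patients, 27 HPV+, so 41 − 27 = 14 HPV-) and 100% in the validation cohort (33 patients, 20 HPV+, so 33 − 20 = 13 HPV-).

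- Test cohort: 13/14 = 92.9%, and 48 × 13/14 = 44.6.
- Validation cohort: 13/13 = 100%, and 48 × 1 = 48.
- Pooled: 26/27 = 96.3%, and 48 × 26/27 = 46.2.

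About 45 to 48 of the 48 controls would therefore be negative at baseline.

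**4. HPV+ patients undetectable at baseline**

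Pilot baseline sensitivity was 100% of 27 and 90% of 20 (section 2).

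- Test cohort: 0/27 undetectable, and 143 × 0 = 0.
- Validation cohort: 2/20 = 10%, and 143 × 0.10 = 14.3.
- Pooled: 2/47 = 4.3% (exact 95% CI 0.5% to 14.5%), and 143 × 2/47 = 6.1 (0.7 to 20.8 over the interval).

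By cohort rate this is about 0 to 14 of the 143 registered. About 143 − 14 = 129 up to 143 could contribute a percentage change, before losses from missing baselines.

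**5. HPV+ patients with no baseline sample**

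The protocol gives no rate, so this group cannot be sized. It arises only in the HPV+ cohort, because controls without a baseline sample are withdrawn.

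**The case against.** The strongest reply is that the kinetics endpoint is about HPV+ patients, and for them it works. They are sampled before, weekly during and shortly after treatment, and on the pilot rates 90% to 100% should have a detectable baseline. This stands. A reader might infer that the endpoint as a whole cannot be produced; the documents do not support that.

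Second, the controls are not without data. They have baseline and 6-week-onward samples, section 12.2.2 refers to every assessment, and the protocol does not define how soon after treatment counts as immediate. This also stands in part: a sparse control plot is possible. It would still hold nothing on treatment and nothing in the first 4 weeks.

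Third, rules for undetectable or missing values usually belong in the SAP, to which section 12.3 defers full details. That is fair as far as the rules go. But the protocol itself fixes percentage change as the measure and commits to an HPV- display, and an SAP could only depart from that text.

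Fourth, a negative call rests on thresholds from the pilot (section 11.3.1), so a negative baseline need not be exactly zero. This is correct, which is why the measure is called undefined or uninformative. The documents give no detection limit or precision, so no figure can be put on instability near the limit.

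A reader might also infer that losing low-level patients makes the clearance curve misleadingly selective. The documents do not show this. A patient with nothing detectable at baseline has no clearance to display, and the number affected may be zero.

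**Conclusion.** The inconsistency is real but minor. As written, the HPV- display has no data during RT/CRT or in the 4 weeks after it. The fixed measure is undefined or uninformative for about 45 to 48 of 48 controls, for about 0 to 14 of 143 HPV+ patients, and for an unknown number of HPV+ patients kept without a baseline sample.

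These counts assume that the pilot's baseline accuracy carries over to this study and that all 143 and 48 patients are registered. The HPV+ count rests on 2 events in 47 patients, so it is imprecise. The denominator is the 143 registered patients, because the 100 evaluable patients in section 12.1 are defined for the primary endpoint.

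The kinetics can still be shown for most HPV+ patients. The endpoint is descriptive, and the primary specificity analysis and the sample size are unaffected.

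**What to change.** Reconcile sections 1, 8.1, 8.2.2, 12.2.2 and 12.3 as follows.

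- Limit the on-treatment and early post-treatment kinetics display to HPV+ patients.
- Plot individual and median log10 HPV DNA levels over time for all HPV+ patients with samples. Place undetectable values at the detection limit, which the laboratory would have to supply, and include patients without a baseline from their first sample.
- Report the proportion undetectable at each visit next to the plot.
- Keep percentage change as a supplement in HPV+ patients with a measured, detectable baseline, and state how many are excluded and why.
- For HPV- patients, report the proportion HPV-detect positive at baseline, 6 weeks and 3, 6, 9 and 12 months.

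Restricting the whole kinetics analysis to patients with a detectable baseline would be simpler. It would, however, drop the very patients with an undetectable or missing baseline for whom the present measure fails, so plotting levels for all HPV+ patients is preferable.

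The cost is revised wording and a different plot. No extra samples, visits or patients are needed.
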